## 3. STUDY DESIGN

### 3.1. Overall Design and Plan

- Single-arm, open-label, phase II study of vosaroxin in combination with cytarabine in patients with newly diagnosed AML.
- Vosaroxin will be administered intravenously at 90 mg/m^2 on days 1 and 4. Cytarabine will be administered in standard fashion as a continuous infusion of 100 mg/m^2 daily on days 1-7.
  - Patients with evidence of residual leukemia on “Day 14 biopsy” following initial induction will be offered re-induction with intravenous vosaroxin at 70 mg/m^2 on days 1 and 4 in combination with continuous infusion cytarabine at 100 mg/m^2 daily on days 1-7.
- Two-stage design. Forty-one (41) patients will provide 80% power to detect a 20% increase in complete remission rates (from 40% to 60%) with a Type I Error rate of 5%. The design permits one interim look to examine evidence of futility after the first 17 patients are evaluable for response. If  $\leq 7$  patients achieve CR then the likelihood of reaching the goal endpoint of  $\geq 60\%$  remission would be diminished. In this case, the DSMB (consisting of a representative from the funding organization, the study chairs, a biostatistician, and participating investigator to be selected by the study chairs) will review the clinical data to determine the merits of continued enrollment. If  $> 7$  CRs are observed then the second stage will open automatically and increase enrollment to 41 patients.
  - Stage 1: First 17 patients who are evaluable for response prior to futility analysis
  - Stage 2: Patients 18-41 enrolled after futility analysis
- Likelihood-based assessment of the statistical evidence be used to determine the reliability of the data generated and will provide the option of adding one or two extension cohorts of 10 participants each if the initial trial results are inconclusive.

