### 12.3. Study Design

*Overview:* Two-stage single-arm phase II designs with a single interim look for futility are common in this setting. Simon’s optimal two-stage design is a classic design and remains a popular choice. Herein we propose, in the context of a standard two-stage design, that a likelihood-based assessment of the statistical evidence be used. The unique and informative assessment of the observed evidence provided by likelihood ratios is reason enough to employ the approach.

We will employ the likelihood ratio (LR), not a tail area probability (p-value), to represent the strength of statistical evidence with respect to either a 40% or 60% true CR rate. Likelihood ratios are positive and a LR of 1 indicates completely neutral evidence. Small likelihood ratios ( $LR \ll 1$ ) indicate evidence for the null hypothesis and large likelihood ratios ( $LR \gg 1$ ) indicate evidence for the alternative. The scale of evidence is truly continuous, mapping a gradual shift from weak to moderate to strong evidence.

An important advantage is that, unlike p-values, likelihood ratios have three evidential zones: evidence favoring the null hypothesis, evidence favoring the alternative hypothesis, and weak or inconclusive evidence (i.e., favoring neither hypothesis). Of course, p-values have only two zones: evidence against the null hypothesis ( $p < 0.05$ ) and inconclusive evidence ( $p > 0.05$ ; large p-values do not constitute stronger evidence in favor of the null hypothesis). Moreover, the likelihood false discovery rate is easily quantifiable as  $1/(LR+1)$ . Thus, an observed likelihood ratio of 4 (supporting the alternative) has a false discovery rate of 20%. Lastly, likelihood designs have excellent operating characteristics.

*Parameters and assumptions:* For planning purposes, we assume the complete remission rate of standard induction chemotherapy is 40% in the targeted population of this trial and that the use of Vosaroxin in combination with cytarabine may increase this rate to 60%. We plan to enroll a total of 41 patients, but provide the option of adding an extension cohort of 10 to 20 participants if the initial trial results are inconclusive.

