*Two-stage single-arm phase II designs:* There are many two-stage designs that meet nominal Type I and II Error criteria. We choose a two-stage design with a slightly increased expected sample size (EN) of 25.6 but keeps the two-stage sample size below that of a single-stage study ( $n=42$ ) as follows: In stage I, 17 patients are accrued and the study is stopped only if 7 or fewer patients experience a complete remission (CR). Stopping in this fashion is interpreted as evidence of futility. If 8 or more patients experience a CR, the study continues to accrue an additional 24 participants (for a total of 41). At the end, the study is said to generate evidence in support of the hypothesis that incorporating Vosaroxin into frontline AML induction chemotherapy is worthy of future study if 22 or more patients experience CR (i.e. if the observed response rate is greater than 53%). If frontline induction therapy with Vosaroxin plus standard dose continuous infusion cytarabine fails to improve upon the historical CR rate of 40% with conventional 7+3 induction therapy, the study has a 64% probability of early termination (PET).

A standard (frequentist) two-stage design is unable to handle deviations from its planned design (i.e., when the sample size is anything other than 17 or 41). This occasionally happens in multi-center clinical trials for practical reasons relating to the speed of communication and clinical expediency. Green and Dahlberg introduced flexible designs to that are able to accommodate such deviations from planned designs with minimal impact to their nominal operating characteristics. However, in this case, the Green and Dahlberg criteria result in a 25% PET, which poorly protects patients from ineffective therapy. This is one motivating factor in our choice of employing a likelihood-based assessment of the evidence. The likelihood ratio reveals alternative interim stopping criteria that maintain nominal Type I and Type II Error rates, adding significant logistic flexibility (Table 6). Within the context of standard two-stage design, we believe our proposed design best balances the probability of early termination and expected sample size under the stated constraints.

**Table 6.** Interim stopping rules that are constrained to lie between 30% and 60% of total accrual and have a probability of early termination that exceeds 50%. Type I & II Error rates are below designed nominal levels (5% & 20%).

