Observed CRs in stage I	Stage I sample size	Probability of early termination	Expected sample size	Likelihood ratio favoring null that corresponds to Simon's futility stopping rule
7	17	64%	25.6	1/3.375
8	19	67%	26.3	1/3.375
9	21	69%	27.2	1/3.375
10	23	71%	28.2	1/3.375
6	16	53%	27.8	1/5.062
7	18	56%	28.2	1/5.062
8	20	60%	28.5	1/5.062

*Likelihood assessment of evidence:* In accordance with our desire to maintain a uniform study design, we set a total sample size of 41 participants, a 17 patient first stage, and an interim futility criterion of 7 or fewer CRs with the added flexibility at the interim analysis indicated in table 1. The interim futility criterion translates to stopping the study at the end of the first stage if the observed likelihood ratio is less than 1/3.375 (i.e., if the evidence better supports the null hypothesis by a factor of at least 3.375). The likelihood ratio is defined as  $LR = \theta_1^r (1 - \theta_1)^{n-r} / \theta_0^r (1 - \theta_0)^{n-r}$  where  $r$  is the number of CR's among  $n$  patients treated and  $H_0: \theta = \theta_0 = 0.4$ ,  $H_1: \theta = \theta_1 = 0.6$ . The translated stopping LR's for the competing designs are listed in the last column of table 1.

An important aspect of the likelihood assessment is that it can quantify the reliability of an observed outcome. For example, while the study would stop early with either an observed LR of 1/3.375 or 1/15 (evidence favoring the null hypothesis), the associated false discovery rates of 0.23 (=1/4.375) and 0.063 (=1/16), respectively, distinguish between those results and provide critical information for investigators when interpreting this evidence at the end of the study.

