LR Class	Trials at end of two-stage design	Weak evidence	Add 10 patients	Weak evidence	Add 10 patients	Weak evidence
$LR \leq 1/3.375$	1145		207		105	
$1/3.375 < LR < 1$	260	424 (8.5%)	113	179 (3.6%)	35	58 (1.2%)
$1 < LR < 3.375$	164		66		23	
$LR \geq 3.375$	247		38		16	
Results under true Ha:						
$LR \leq 1/3.375$	143		39		16	
$1/3.375 < LR < 1$	148	397 (7.9%)	48	135 (2.7%)	30	134 (1.1%)
$1 < LR < 3.375$	249		87		26	
$LR \geq 3.375$	4026		223		63	

a 64% (3184) and 8.7% (434) trials stopped early for futility under the true null and true alternative hypotheses, respectively.

Under the likelihood evidentiary paradigm observed results are reported as follows (let  $K > 1$  be the pre-specified LR that maintains a certain false discovery rate): 1) sufficiently strong evidence for the null ( $LR \leq 1/K$ ); 2) actionable weak evidence for the null ( $1/K < LR < 1$ ); 3) actionable weak evidence for the alternative ( $1 < LR < K$ ); 4) sufficiently strong evidence for the alternative ( $LR \geq 1/K$ ). We will also report the FDR for the result at hand, i.e.  $1/(LR+1)$ . As detailed below, this trial may recruit additional participants if the observed LR is weak (i.e.,  $1/K < LR < K$ ) with a maximum of 61 participants.

A significant number (~8%) of discoveries under the null and alternate hypotheses for our two-stage design had LR of exactly 3.375. Though such results would allow the conclusion of sufficient activity to warrant further investigation in more definitive trials because it passes nominal Type I and II Error rate criteria, we propose to further evaluate these results in the extension cohorts by setting  $K=4$ , treating those trials with LR's of 3.375 as weak evidence. The PET remains unaffected by this slight change. However, the design that uses  $K=4$  and a total sample size of 61 patients has a false positive rate that decreases to 3.7% and power that increases to 83.7%. This strategy also decreases the false discovery rate to 3.9% (table 8). Hence such a design is quite feasible.

**Table 8.** Simulation results for extending the likelihood two stage trial for the purpose of refining weak evidence for K=4. Cells contain the number (proportion of 5000) trials in each evidentiary class.

Results Under True Ho:						
LR Class	Trials at end of two-stage design	Weak evidence	Add 10 patients	Weak evidence	Add 10 patients	Weak evidence

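### The likelihood-ratio form of the interim rule uses a strict inequality that does not stop at 7/17, the boundary its own count rule stops at, and two fallback rules in Table 6 sit marginally above the 5% limit claimed for them (minor)

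*Combined protocol and SAP*

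**What the plan says.** Section 12.3 gives the interim rule in two forms.

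- **Count form.** After 17 patients "the study is stopped only if 7 or fewer patients experience a complete remission (CR"). Table 6 attaches to this rule a 64% probability of early termination (PET), an expected sample size of 25.6 and an LR of 1/3.375.
- **LR form.** The paragraph on likelihood assessment translates the count rule into "stopping the study at the end of the first stage if the observed likelihood ratio is less than 1/3.375". A parenthesis in the same sentence restates this as evidence favouring the null by a factor of 3.375 or more. The next paragraph gives an LR of 1/3.375 as an example of a result that stops the study.

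The caption of Table 6, which lists fallback rules for interim looks at other sample sizes, says "Type I & II Error rates are below designed nominal levels (5% & 20"%).

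After Table 7, Section 12.3 defines an LR strictly between 1/K and K as weak and says "this trial may recruit additional participants if the observed LR is weak", up to 61 participants. It then sets K=4 and adds "The PET remains unaffected by this slight change".

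The Synopsis (Study Design and Statistical Plan), Section 3.1 and Section 12.2 treat 7 or fewer remissions differently: that count leads to a DSMB review of whether enrolment should continue.

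**The concern.** A pre-specified stopping rule should give one answer at its boundary. Here the boundary count is also the single most likely stage I result if the regimen is no better than the historical rate. The LR form matters beyond the planned 17 patients, because Section 12.3 offers it as the tool for an interim look that falls at another sample size. Four of the seven rules in Table 6 (7/17, 8/19, 9/21 and 10/23) have an LR of exactly 1/3.375, so the strict wording fails at the boundary of each.

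At stake are the protection against continuing with an ineffective regimen and the 5% type I error. The plan itself sets aside the Green and Dahlberg criteria because they give only a 25% PET, so a fall in PET is a cost by its own standard. The Table 6 caption is a separate and smaller matter: it claims an error-rate property that two of the listed rules do not strictly have.

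**Working it through.** **Inputs.** Null rate: "we assume the complete remission rate of standard induction chemotherapy is 40% in the targeted population of this trial" (Section 12.3). Alternative: the new combination "may increase this rate to 60"% (Section 12.3). Nominal error: the design is described "with a Type I Error rate of 5"% (Section 3.1). Success: 22 or more remissions of 41 (Section 12.3).

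**Formulas.**

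- With rates 0.4 and 0.6, the plan's LR reduces to 1.5^(2r − n) for r remissions in n patients.
- PET = P(X ≤ r1 | n1, 0.4).
- Expected N = n1 + (1 − PET)(41 − n1).
- Type I error = sum over x > r1 of P(X1 = x) × P(at least 22 − x remissions in 41 − n1 patients), at 0.4. Power is the same sum at 0.6.

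**Step 1: reproduce the plan's design.** Stopping at 7 or fewer of 17 gives PET 64.05%, expected N = 17 + 0.3595 × 24 = 25.63, type I error 4.73% and power 80.1%. This matches the stated 64%, 25.6 and 80%. The simulated 4.9% (247/5000) is within Monte Carlo error, with a standard error of about 0.3 points.

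**Step 2: LR at the boundary.** At 7/17, LR = 1.5^(14 − 17) = 1.5^(−3) = 1/3.375 exactly, which is not less than 1/3.375. At 6/17, LR = 1.5^(−5) = 1/7.59. The strict rule therefore stops only at 6 or fewer. The same exponent, −3, applies to 8/19, 9/21 and 10/23. The even-numbered looks (6/16, 7/18, 8/20) have LR = 1.5^(−4) = 1/5.0625 and are unaffected.

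**Step 3: the strict rule taken literally.** P(exactly 7 of 17) is 19.3% under the null, which is 0.1927/0.6405 = 30% of all futility stops, and 5.7% under the alternative. If 7/17 continues:

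- PET = 0.6405 − 0.1927 = 44.8%.
- Expected N = 17 + 0.5522 × 24 = 30.25.
- A trial continuing from 7/17 needs at least 15 of the next 24, which has probability 2.17% under the null. This adds 0.1927 × 0.0217 = 0.42 points, so type I error is 4.73% + 0.42% = 5.15%.
- Power is 82.9%.

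**Step 4: Table 6, exact, with success at 22 or more of 41.**

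| Rule | PET | Expected N (stated) | Type I error | Power |
|---|---|---|---|---|
| 7/17 | 64.05% | 25.63 (25.6) | 4.734% | 80.1% |
| 8/19 | 66.75% | 26.32 (26.3) | 4.779% | 80.6% |
| 9/21 | 69.14% | 27.17 (27.2) | 4.831% | 81.1% |
| 10/23 | 71.29% | 28.17 (28.2) | 4.888% | 81.6% |
| 6/16 | 52.72% | 27.82 (27.8) | 4.979% | 81.7% |
| 7/18 | 56.34% | 28.04 (28.2) | 5.003% | 82.0% |
| 8/20 | 59.56% | 28.49 (28.5) | 5.033% | 82.3% |

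The type II limit holds in every row. The type I limit is passed by 0.003 points at 7/18 and 0.033 points at 8/20. For 7/18, expected N = 18 + 0.4366 × 23 = 28.04.

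**Step 5: where K=4 applies.** Tables 7 and 8 carry the same early stops, 3184 under the null and 434 under the alternative. In Table 8 the end-of-trial classes plus early stops sum to 878 + 527 + 286 + 125 + 3184 = 5000 and 65 + 226 + 607 + 3668 + 434 = 5000. Trials stopped at the interim, including those at 7/17, therefore never enter the weak-evidence branch, and the PET is indeed unchanged.

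**Step 6: if the interim does not bind.** If a count of 7 or fewer never stops the trial, success at 22 or more of 41 has type I error 5.32% and power 83.9%. This is the upper limit for an advisory interim.

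**The case against.** The strongest reply is that nobody would apply the strict version. The sentence presents itself as a translation of the count rule, its parenthesis includes equality, the next paragraph stops at 1/3.375, Table 6 pairs 7/17 with that value, and the stated PET and expected sample size reproduce only if 7/17 stops. All of this stands. It makes the fault a slip of wording and the Step 3 figures the consequence of a literal reading, not a forecast. It does not make the sentence right, and the LR form is the one meant for unplanned interim sizes.

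A reader might go further and infer that K=4 turns a 7/17 stop into a weak result that can be extended, because 1/3.375 lies between 1/4 and 1. The documents do not support this. Section 12.3 brings in K=4 for completed two-stage trials with an LR of exactly 3.375, describes patients as added at the end of the trial, and leaves early stops untouched in Table 8. The 61 maximum is 41 + 20. Nor would that reading inflate type I error: with K=4, 22/41 counts as weak, so success at 41 needs 23 remissions (LR 1.5^5 = 7.59), and even with stopping only at 6 or fewer of 17 the type I error is 2.65% at 41 and 3.76% after extension to 61. What remains is that the extension sentence does not itself name a stage.

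The Table 6 excesses are fairly called trivial: 5.003% rounds to 5.00%, and neither changes a decision. They do not justify dropping rules that exist to give logistic flexibility.

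**Conclusion.** The point holds as a minor correction. The LR form of the interim rule is wrong as written at its boundary, a result with 19.3% probability under the null. Read literally, it gives PET 44.8%, expected N 30.25 and type I error 5.15%, against 64%, 25.6 and 4.73% for the intended rule. The design as intended and simulated is sound, and the statement that K=4 leaves the PET unaffected is correct. The Table 6 caption is untrue for two rows by at most 0.033 points, and one expected sample size is off by about 0.2; both are corrections of record.

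The more consequential inconsistency at the same boundary is that Section 12.3 stops the study at 7 or fewer of 17, while the Synopsis, Section 3.1 and Section 12.2 send that count to the DSMB. The stated PET and error rates assume a stop. These passages must be reconciled; the documents do not settle which governs.

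The figures rest on exact binomial calculation at 40% and 60% and, except where K=4 is named, on success at 22 or more of 41.

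**What to change.** - In the likelihood paragraph of Section 12.3, replace the strict inequality with LR ≤ 1/3.375 (7 or fewer of 17).
- In the extension sentence after Table 7, add that K=4 and the extension apply only to trials that reached 41 patients, as Table 8 already assumes. Leave the PET statement as it is.
- In Table 6, keep all seven rows, change the caption to say that type I error is at most 5.04% with success at 22 or more of 41, and correct the expected sample size for 7/18 from 28.2 to 28.0.
- Reconcile the Synopsis, Section 3.1 and Section 12.2 with Section 12.3 on what follows 7 or fewer remissions. If the interim is non-binding, state that type I error at 22 or more of 41 can be up to 5.32%.

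The first three changes are wording only: they need no further patients and leave the intended design as it is. The fourth requires the sponsor to decide the status of the interim and, if it is advisory, to quote the higher type I error.

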### 12.2. Sample Size Considerations

In accordance with our desire to maintain a uniform study design, we set a total sample size of 41 participants. An interim futility analysis will be conducted following enrollment of 17 evaluable patients. If  $\leq 7$  patients achieve CR then the likelihood ratio in support of reaching the goal endpoint of  $\geq 60\%$  remission would be diminished and the data would then be reviewed by a DSMB to determine if further enrollment is warranted. If  $> 7$  CRs are experienced by the first 17 evaluable patients, enrollment will automatically proceed to enroll a total of 41 patients. Under this two-stage design, a 60% complete remission rate by the “7+V” combination is at least 3.375 times more likely than a 40% CR rate if 22 or more patients experience CR.

In the context of the planned likelihood assessment the option will be provided to add an extension cohort of up to 20 participants if the initial trial results are inconclusive. The use of a likelihood based extension cohort results in false positive and false discovery rates of 3.7% and 3.9%, respectively.

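### The 3.7% false positive rate stated for the K=4 extension design does not match Table 8, which gives 3.4%, or the 3.9% FDR and 83.7% power stated with it (minor, conservative).

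*Combined protocol and SAP*

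**What the plan says.** Section 12.3 sets the hypotheses. For the null, "we assume the complete remission rate of standard induction chemotherapy is 40"%; vosaroxin with cytarabine "may increase this rate to 60"%. On the interim rule it says "In stage I, 17 patients are accrued and the study is stopped only if 7 or fewer patients experience a complete remission (CR"); otherwise "the study continues to accrue an additional 24 participants (for a total of 41").

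The same section then raises the evidence threshold to K=4, "treating those trials with LR's of 3.375 as weak evidence". A trial that is still weak can be extended in steps of 10, "with a maximum of 61 participants". For this design it states "a false positive rate that decreases to 3.7% and power that increases to 83.7"%, and the next sentence gives an FDR of 3.9% with a reference to Table 8.

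Section 12.2 says that the extension "results in false positive and false discovery rates of 3.7% and 3.9%, respectively". The statistical plan in the synopsis gives the same pair of figures.

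Table 8 reports 5000 simulated trials under each hypothesis. Its footnote counts 3184 early stops for futility under the null and 434 under the alternative.

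**The concern.** The extension allows patients to be added after an inconclusive result has been seen, so a reader will want to know what it does to the false positive rate. The plan answers with 3.7%, in three places. That figure cannot be recovered from the table that reports the simulation, and it does not fit the FDR and power given with it. Anyone who checks the plan, or carries the figure into a report, will find that the text and the table disagree. At stake is the accuracy of a stated operating characteristic. The design itself is not affected.

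**Working it through.** **Inputs (section 12.3 and Table 8)**

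- CR rate 0.40 under the null and 0.60 under the alternative.
- Stage 1: 17 patients, stop at 7 or fewer CRs. Analyses at 41, 51 and 61 patients.
- K = 4.
- Table 8 counts with LR of at least 4, at 41, 51 and 61 patients: 125, 32, 15 under the null; 3668, 342, 176 under the alternative.

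**1. The plan's own convention, checked on Table 7 (K=3.375)**

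The false positive rate and the power are cumulative successes divided by 5000. The FDR is false positives divided by all positives.

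- False positive rate: (247+38+16)/5000 = 301/5000 = 6.0%. The text says 6%.
- Power: (4026+223+63)/5000 = 4312/5000 = 86.2%. The text says 86%.
- FDR at the end of stage II: 247/(247+4026) = 5.8%. The text says 5.8%.

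The convention reproduces the Table 7 text.

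**2. The same convention on Table 8**

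| Quantity | From Table 8 | Stated |
|---|---|---|
| Power | (3668+342+176)/5000 = 4186/5000 = 83.7% | 83.7% |
| FDR | 172/(172+4186) = 3.947% | 3.9% |
| False positive rate | (125+32+15)/5000 = 172/5000 = 3.44% | 3.7% |

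Only the false positive rate fails to reproduce. The gap is 3.70 − 3.44 = 0.26 points.

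**3. Consistency of the three stated figures without the table**

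- 3.7/(3.7+83.7) = 4.2%, not 3.9%.
- In reverse, with 83.7% power, an FDR that prints as 3.9% (3.85% to 3.95%) needs a false positive rate of 0.837 × FDR/(1 − FDR), which is 3.35% to 3.44%.
- A rate of 3.7% is about 185 false positives in 5000. The printed FDR fits 172.

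**4. Are the Table 8 cells intact?**

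- Null, 41 patients: 3184+878+527+286+125 = 5000. Extensions: 307+299+175+32 = 813, and 186+175+98+15 = 474.
- Alternative, 41 patients: 434+65+226+607+3668 = 5000. Extensions: 20+170+301+342 = 833, and 21+85+189+176 = 471.

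Every column closes on 5000 or on the preceding weak-evidence count, so a misread success cell is not a plausible explanation.

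**5. Exact calculation**

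With these two rates, the plan's likelihood ratio reduces to LR = 1.5^(2r−n) for r CRs in n patients. At odd n, LR of at least 4 needs 2r−n of at least 5, that is 23/41, 28/51 or 33/61. Binomial recursion through the stages gives:

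| Condition | False positive rate | Power | FDR |
|---|---|---|---|
| Stop at 7 or fewer of 17 is binding | 3.45% | 83.6% | 4.0% |
| Interim review never stops the trial | 3.9% | 88.9% | 3.9/(3.9+88.9) = 4.2% |

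With the binding stop, cumulative success by analysis is 2.51%, 3.13% and 3.45% under the null, and 72.6%, 79.8% and 83.6% under the alternative.

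**6. Other readings tried**

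| Reading | False positive rate | Power |
|---|---|---|
| One jump from 41 to 61 (exact) | 3.1% | 82.9% |
| Stop at 6 or fewer of 17 (exact) | 3.8% | 87.3% |
| Unresolved trials dropped from the denominator (Table 8) | 172/4727 = 3.6% | 4186/4726 = 88.6% |
| Unresolved trials with LR between 1 and 4 counted as successes (Table 8) | (172+98)/5000 = 5.4% | not needed |

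None gives 3.7% together with 83.7%.

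**The case against.** Four points can be made for leaving the text alone.

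**The error is in the safe direction.** The stated rate exceeds the tabulated one and both are below 5%. The claims in section 12.3 that the rate falls and that the design is feasible hold equally well at 3.4%. This stands, and it is why the point is minor. A reader might infer from a wrong error rate that the extension fails to control Type I error, or that the design needs changing. The documents support neither.

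**It is within simulation noise.** With 5000 trials the Monte Carlo standard error is √(0.0344 × 0.9656/5000) = 0.26 points, about the size of the gap. If the true rate is 3.45%, a run with 185 or more false positives has a probability of about 18%. Section 12.3 also attaches its Table 8 reference to the FDR sentence, not to the sentence with the 3.7%. This stands as a possible origin. A reader might infer that the exact 3.45% proves 3.7% impossible; it does not. But the plan presents no other run, and another run would not explain an FDR that fits 172 false positives.

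**The rate depends on the interim action.** The synopsis and sections 3.1 and 12.2 send 7 or fewer CRs to DSMB review of continued enrollment, while section 12.3 describes a stop. Between always stopping and never stopping, the exact rate runs from 3.45% to about 3.9%, and 3.7% lies inside. This stands as a condition to state with any corrected figure. It does not rescue the 3.7%: Table 8 counts the early stops, so it assumes the stop, and without the stop power is 88.9%, not 83.7%.

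**Exact values would create a new mismatch.** Changing power to 83.6% and FDR to 4.0% in the text alone would make both disagree with Table 8. This stands. A reader might infer that those two figures are wrong as well; they reproduce from the table and should be left.

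**Conclusion.** Wrong as written, minor. The 3.7% in the synopsis and in sections 12.2 and 12.3 should read 3.4% to match Table 8. The conclusion rests on the Table 8 counts, which balance, and on the plan's own convention, which reproduces the Table 7 text and the other two K=4 figures.

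The overstatement is about 0.26 percentage points, or 0.26/3.7 = 7% of the stated value. The corrected figure assumes the stage 1 stop is applied, as Table 8 does. How the 3.7% arose cannot be determined from the documents.

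**What to change.** - Replace 3.7% with 3.4% in the synopsis (statistical plan), section 12.2 and section 12.3, and cite Table 8 as its source. Alternatively, supply the simulation run that gave 3.7%, with the power and FDR from that same run.
- Add one sentence: the figure assumes the study stops at 7 or fewer CRs in 17 patients (exact rate 3.45%), and it would be about 3.9% if the interim review never stopped the trial.
- Leave power at 83.7% and FDR at 3.9%. If the sponsor prefers exact values (3.45%, 83.6% and 4.0% with the stop binding), Table 8 must be replaced at the same time.

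The cost is one number changed in three places and one added sentence. The design, the boundaries and the sample size are untouched.
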